Sauna post-fire incident exposure detoxification was performed post 9-11 and studied in research published in 2006 by Cecchini, etal., (article attached) but the results of the study are incomplete and were not controlled. Crinnion, 2007, as director of the Environmental Medicine Center of Excellence at the Southwest College of Naturopathic Medicine in Tempe, Arizona, summarized that saunas, "...can be used very effectively for certain cardiovascular problems and as a means to enhance the mobilization of fat-soluble xenobiotics. When saunas are used to reduce blood pressure and enhance blood flow and cardiac functioning, only short sauna sessions (15 minutes) are necessary.

A traditional sauna generates heat by heating rocks to heat the air, adding in steam to heat the skin, and generally operate at 180-190 deg F. An infrared sauna uses light to create heat that warms your body directly without warming the air and operate at lower temperatures, 110-140 deg F. A Mayo Clinic Consumer Health report by [name] A Bauer, MD, accessed 12/21/2017 (attached) reported "...no adverse effects have been reported with infrared saunas."

The purpose of the current study is to determine if treatment in an infrared sauna: a) affects absorption of PAHs as measured by urinary metabolites; and b) changes core body temperature and heart rate. Infrared exposure from the sauna treatment is expected to increase the core body temperature, which may have a detrimental effect on the firefighter performance; heart rate will be used as a measurement of stress. There is sparse literature concerning the subject of using infrared sauna as a post-exposure treatment.

2) Purpose

The purpose of the current study is to determine if post-fire training exercise treatment in an infrared sauna as compared to the standard post-fire treatment:

- a) Affects absorption of PAHs as measured by urinary metabolites. (Aim 1)
- b) Changes core body temperature and heart rate. (Aim2)

These two aims will be achieved by the following objectives:

- a. Coordinating with the Fire Department to recruit and consent firefighters scheduled for training fires to participate
- b. Obtaining 12 hour pre and post-fire urine samples, along with dermal samples.
- c. Monitoring core body temperature and heart rate at baseline, during fire response, and for 8 hours after
- d. Splitting the post-fire post-standard Rehab firefighters into 2 groups: no additional treatment group or sauna rehab group.

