 - 8. **(For Stage 2 fires only)** The subjects will then be randomized to either an infrared sauna treatment, or no additional treatment following their fire department protocols. The firefighters will be randomized by the UA study team as such: Firefighters will pull a piece of paper out of a helmet; if it says "sauna" they will participate in the sauna treatment. If it is blank, they will participate in no additional post-fire treatment. "Sauna treatment" consists of a firefighter entering the sauna for 20 minutes as soon as the fire department has completed their standard rehab.
 - 9. Following the sauna treatment or no additional treatment time period, dermal wipes of the left calf, arm, and neck will be repeated and the subjects will complete a survey and return to work. The dermal wipe samples will be transported under Arizona Department of Transportation guidelines for transportation of samples to the University of Arizona.
 - 10. Core temperature and heart rate will continue to be monitored for up to 8 hours after training scenario. At the end of the 8 hour period, the firefighter will turn the monitor off by pressing the "stop" button and the "On/Off" button.
 - 11. The subjects will collect all their urine after the fire training for a period of up to 12 hours in the same manner that urine was collected prior to the fire training.
 - 12. End of sampling period: At the end of the sampling period, the UA study team will, again, meet the firefighters at the fire department to collect the data recorder/heart rate monitor data recorder, Polar Heart Rate belt, and urine samples.
 - 13. The urine will be stored at the Medical Research Building at -80 deg C until analyzed for urinary PAH metabolites and potentially other toxicants from the fire, and, dependent on the available budget, similar evaluations may be carried out on the skin wipes. The core

temperature and heart rate data will be downloaded from the data recorder onto a password protected computers and will be analyzed for comparison to the pre-fire data. The personal air monitors will be downloaded in the same manner and analyzed for air quality.

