- Infrared Sauna: No adverse effects have been reported with infrared saunas
- Core Body Temperature/Heart Rate monitoring: In accordance with the CorTemp User Manual, page 6, use of the CorTemp ingestible temperature sensor is contraindicated for the following conditions:
 - In any subject whose body weight is less than eighty (80) pounds.
 - In the presence of any known or suspected obstructive disease of the gastrointestinal tract, including but not limited to diverticulitis and inflammatory bowel disease.
 - In any subject exhibiting or having a history of disorders or impairment of the gag reflex.
 - In any subject with previous gastrointestinal surgery.
 - In any subject having felinization* of the esophagus.
 - In any subject who might undergo Nuclear Magnetic Resonance (NMR)/Magnetic Resonance Imaging (MRI) scanning during the period that the CorTemp Core Body Temperature Sensor is within the body.
 - In any subject with hypomotility disorders of the gastrointestinal tract, including but no limited to ileus.
 - In any subject having a cardiac pacemaker or other implanted electromedical device.

^{*}Felinization=Transient transverse folds of the esophageal mucosa as seen by barium esophagography and on endoscopic examination have been termed "felinization." This finding has been considered a normal variant or has been associated with reflux esophagitis. No symptoms have been associated with its presence.

Additionally, the CorTemp Core Body Temperature Sensor may not be appropriate in individuals who have experienced swallowing disorders. If an individual experiences difficulty swallowing the sensor, they may not be a candidate for the study.

The minimal risk will be mitigated by having all participants complete a contraindications form at the time of consenting and then reviewing their form prior to swallowing the pill. Any firefighter who indicates they suffer from one or more of the contraindications will be excluded from the study. The contraindications form has been clinically verified by [name] and found to be an adequate screening tool to ensure the safety of study participants. Additionally, if any participants experience difficulty swallowing the sensor, they will be excluded from the study.

11) Potential benefits to subjects and/or society

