The fire department's training fire is a required training exercise, but the research concerns the comparison of the post-fire sauna treatment versus the standard (no-sauna) treatment post-fire. The data from the core body temperature/heart rate monitor data recorder will be downloaded within 48 hours and examined for excessive core body temperature rise (above 102 Deg F) by the PI, [name]. The firefighter, after exiting the sauna, will have blood pressure pulse readings taken and documented as part of the fire department's post-fire treatment protocols. Firefighters who do not participate in the sauna treatment will be monitored and the data downloaded in a likewise time period, but the data will not be examined by [name] until the data are analyzed by statistical methods as the standard treatment is not being changed by the study from what the fire department normally performs on its firefighters during their normal annual fire training exercises.

16) Withdrawal of subjects

It will be made clear to the firefighters that their participation is voluntary and that they may withdraw on their own volition at any time. It is not anticipated that the PI or other UA study team members will have to withdraw a subject after the consent and verification of the contraindication form. However, there is potential that the firefighter may become not medically fit for duty for an unrelated reason between the consenting and sampling period. This situation would result in the subject being withdrawn from the study.

In addition, in order to adequately achieve the end total of up to 24 firefighter participating in the Stage 2 exercise, it may become imperative to consent more than 24 firefighters. When the time is reached that 24 firefighters have been evaluated for the Stage 2 training fire testing, additional testing of firefighters who consented but haven't been tested will be stopped and the untested firefighters will be withdrawn from the study.

17) Sharing of results with subjects

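### Section 10 omits the core-temperature rise that section 1 expects from the sauna, and neither arm is asked about symptoms or effects on duty after return to work

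*Protocol*

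**What the plan says.** **Risk statement.** Protocol section 10 gives one line for the infrared sauna: "No adverse effects have been reported with infrared saunas". The same sentence stands in section 1 (Background) as a quotation from a consumer health report. Section 10 repeats it without naming that source.

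**Expected effect.** The next paragraph of section 1 says: "Infrared exposure from the sauna treatment is expected to increase the core body temperature, which may have a detrimental effect on the firefighter performance". It adds that heart rate will serve as a measure of stress and that literature on the sauna as a post-exposure treatment is sparse.

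**Physiological monitoring.** Section 8, step 10, records core temperature and heart rate for up to 8 hours after the training scenario, in both arms. Under section 15 the sauna arm's data are downloaded within 48 hours and "examined for excessive core body temperature rise (above 102 Deg F) by the PI". Blood pressure and pulse are taken and documented after the sauna. The no-sauna arm's data are not examined by the PI until the statistical analysis.

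**Contact with the firefighter.** In step 9, after the sauna or the equivalent period, "the subjects will complete a survey and return to work". Section 3 describes the survey as covering demographics, exposures before the fire, job duties and unspecified other information. In step 12 the study team will "meet the firefighters at the fire department to collect the data recorder/heart rate monitor data recorder, Polar Heart Rate belt, and urine samples". Section 14 tells an injured subject to seek treatment and describes no report to the study.

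**The concern.** The protocol names a possible harm in one place, screens for its physiological marker in another, and leaves it out of the section meant to state the risks. A general sentence about saunas does not describe this use: 20 minutes in the sauna straight after live-fire training and standard rehab, followed by return to work.

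The harm section 1 has in mind is impaired performance. That would show in the hours after the sauna, when the firefighter is back on duty and still wearing the recorder. In that window the plan collects temperature and heart rate but describes no question about how the firefighter felt or worked. A trace can show a rise. It cannot show dizziness, faintness or an effect on duty.

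The stake is the use of the result. Section 3 says the department would like to add the sauna to its rehab procedure, and section 17 says it will receive the aggregate results. If no one is asked, silence about symptoms could be taken as reassurance that it does not give.

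**Working it through.** The point rests mainly on the text. The protocol states no adverse-event rate and plans no power analysis (section 6), so there is no figure of its own to reproduce.

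**Step 1: risk entry against expectation.**

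| Place | Content on the sauna |
|---|---|
| Section 1, report quoted | No adverse effects reported |
| Section 1, purpose paragraph | Core-temperature rise expected; may harm performance |
| Section 10 | No adverse effects reported; nothing else |
| Section 15 | Sauna-arm data examined for a rise above 102 deg F |

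Section 10 carries over the first row and drops the second, although section 15 acts on it.

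**Step 2: what is captured, and when.**

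| Time | Collected | Symptom or duty question described? |
|---|---|---|
| On leaving the sauna | Blood pressure, pulse | No |
| Before return to work (step 9) | Dermal wipes, survey | None named; other information is unspecified |
| After return to work (steps 10, 11) | Temperature and heart rate up to 8 h; urine up to 12 h | No |
| End of sampling (step 12) | Recorder, belt, urine handed over | No |

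Whatever the survey's unspecified items are, its timing rules out events after return to work.

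**Step 3: what a zero count could show if the question were asked.** Stage 2 enrols 20 to 24 firefighters (section 6) and half go to the sauna (section 3), so n is 10 to 12 on the assumption of an even split.

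For 0 events in n, the upper limit of the exact two-sided 95% interval is 1 − 0.025^(1/n):

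- n = 12: 1 − 0.025^(1/12) = 0.265, or 26.5%
- n = 10: 1 − 0.025^(1/10) = 0.308, or 30.8%

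The chance of at least one event with complete ascertainment is 1 − (1 − p)^n. The true rates p are assumed, since the protocol gives none:

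| p | n = 12 | n = 10 |
|---|---|---|
| 5% | 46% | 40% |
| 10% | 72% | 65% |
| 20% | 93% | 89% |

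These figures reflect the sample size, not the gap in collection. They show that zero events would be weak evidence even when every firefighter is asked. When no one is asked, a zero sets no upper limit at all.

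**The case against.** **The anticipated harm is measured.** A reader might infer that harm from the sauna is never ascertained. The protocol does not support that. Temperature and heart rate, the two quantities section 1 names, are recorded past return to work in both arms and compared as Aim 2. A sauna-arm rise above 102 deg F would be seen at the PI's review, and blood pressure and pulse are documented after the sauna. This part of the objection stands, and it limits the gap to symptoms and effects on duty.

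**No claim of zero harm is planned.** A reader might also infer that the study will report harm as absent whatever happens. No passage plans an adverse-event count or a safety conclusion, spontaneous reports remain possible, and section 11 lists whether core temperature rises as something to be learned. The most that can be said is that harms could be missed and that silence would not be evidence.

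**Section 10 and section 1 can both be true.** One sentence describes past reports; the other states an expectation for this setting. It is fair to call section 10 incomplete rather than false. But a risk section that leaves out the one sauna effect the protocol expects and screens for still has to be reconciled with the rest.

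**Some material is not shown.** The survey form and the consent form are not available. The survey may cover symptoms up to the moment it is filled in, and consent may already mention the temperature rise. The first does not reach the period after return to work. The second makes the consent point a check and not a criticism.

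**The aims are unaffected.** Neither part changes the estimates for Aim 1 or Aim 2. That is correct. The gain is in the risk statement and in the safety evidence the department will have.

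**Conclusion.** The point holds in two limited parts. First, section 10 omits the core-temperature rise and possible effect on performance that section 1 expects and section 15 screens for, and these sections must be reconciled. Second, apart from the temperature and heart-rate recording, no symptom or effect on duty is asked about in either arm after return to work. The unasked period runs through up to 8 hours of recording and up to 12 hours of urine collection, in all 20 to 24 Stage 2 firefighters.

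This rests on the procedures as the protocol describes them, and on reading step 12 as a complete list of what happens at that meeting. Collecting adverse events is a protocol procedure, so a statistical analysis plan that is not shown would not close the gap. It is an inexpensive improvement worth making, not a flaw in the main comparison.

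**What to change.** 1. **Complete the sauna entry in section 10.** State the temperature rise and possible effect on performance that section 1 already expects, refer to the section 15 check, and attribute the sentence on no reported adverse effects to its source. Check that the consent form says the same.

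2. **Ask at step 12.** Put one short question, identically worded, to both arms at the existing end-of-sampling meeting: any symptoms, and any effect on duty, since the fire. Report counts by arm with exact two-sided 95% confidence intervals, and set the firefighter's recorded temperature and heart rate beside any event. State with the result that zero events in a group of 10 to 12 is weak evidence.

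**Cost.** A wording change and a few lines on a form, at a meeting that already takes place. The drawback is that firefighters know their arm, so self-reported symptoms may be influenced by it. Identical wording in both arms and the recorded traces help interpretation but do not remove that.
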